5.3. Analysis of Efficacy Variables

5.3.1. Relapse-related variables

Relapse data as assessed by the investigator are stored in SDTM.CE, SDTM.SUPPCE, SDTM.CM and SDTM.FA. The two corresponding SDTM datasets for each study are concatenated for the purposes of this analysis.

For each relapse the corresponding start and stop date/time of symptoms are stored in CE. Whether the relapse meets the criteria for a confirmed relapse is stored in FA.FAORRES (as "Y", "N"), where FATEST = "Relapse Criteria Met".

5.3.1.1. Annualized relapse rate up to end of Analysis Period

The annualized relapse rate (ARR) is defined as the number of relapses per subject-year.

The following variables are derived for the analysis of ARR:

- Number of confirmed/all relapses with start date in the Analysis Period;
- Length of observation for Analysis Period AP3 expressed in years, defined as: [Analysis Period end date Analysis Period start date + 1] in days, divided by 365.25.

These variables are derived for each subject for the Analysis Period AP3 as defined in Section 5.1.9.

In addition, the number of confirmed relapses in each year in AP3 is derived for each subject (i.e., number of confirmed relapses in first year of ponesimod treatment, number of confirmed relapses in second year of ponesimod treatment, etc.). A year is defined as 365 days for this calculation with only the remaining days counted in the last year, e.g., if a subject has 900 days of follow-up, year 3 for that subject will only have 170 days. A similar analysis for the number of unconfirmed and confirmed (all) relapses will be provided.

For the statistical analysis of ARR, the corresponding logarithm of the length of observation is also derived.

For each Analysis Period, relapses are only considered if the start date of the symptoms \geq date of first intake of ponesimod in that analysis period and \leq end date of that analysis period.

5.3.1.2. ARR up to last treatment in the Analysis Period + 7 days

This endpoint was analyzed for the Interim Analysis and is not planned to be analyzed for the Final CSR, as noted below, in Section 5.3.2.4.

For subjects who completed the study at the end of an Analysis Period, who discontinued during an Analysis Period, or who had a treatment interruption between treatment periods, the Analysis Period end date may be up to 90 days after last intake of ponesimod in the Analysis Period.

To consider the on-treatment ARR, ARR up to last treatment date in the Analysis Period + 7 days is also derived.

The number of confirmed relapses and length of observation are derived as defined in Section 5.3.1.1 above, where end of the Analysis Period is capped at the minimum of [last treatment in the Analysis Period + 7 days, end of the Analysis Period] and only relapses with onset

in this period are included. The number of unconfirmed and confirmed (all) relapses is similarly derived.

ARR up to last treatment in the Analysis Period + 7 days is derived for AP3.

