3.4.4.2 Allowed concomitant medications

Administration of intravenous (i.v.) atropine in the event of symptomatic bradycardia.

Vaccination with non-live vaccines is allowed while on study treatment if the vaccination is advised by the primary investigator / treating neurologist, based on her/his clinical assessment of the risk/benefit for the individual patient, and if supported by guidelines for vaccination relevant to this patient population, as applicable.

Ponesimod / ACT-128800 / JNJ-67896153 Multiple Sclerosis		EudraCT 2009-011470-15 EDMS-ERI-206617631
Protocol AC-058B202	Confidential	
Version 12		
15 March 2022, page 63/179		

Patients receiving non-live vaccination against influenza or COVID-19 while on study treatment will have 5 mL of blood drawn prior to and at least 3 weeks after vaccination in order to explore changes in vaccine-specific antibody titers from pre- to post vaccination. Samples will be analyzed at the end of the study at the latest. In case of a vaccine requiring the administration of multiple doses, the post-vaccination sample should be collected at least 3 weeks after the administration of the last dose.

Glatiramer acetate and IFN β -1a are allowed only during study drug interruptions for planned pregnancy. These treatments may be started 7 days after study drug interruption and must be stopped 7 days before study drug re-initiation.

Low dose of corticosteroids (up to 10 mg of prednisone equivalent daily), given as shortterm treatment (up to 2 weeks per treatment cycle with at least 8 weeks' interval between treatment cycles and no more than 4 weeks per year of the study duration on average), and inhaled corticosteroids for pulmonary conditions.

Other treatments considered necessary for the patient's benefit and not categorized as prohibited concomitant medications.

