3.10 Study endpoints

3.10.1 Efficacy endpoints

Only exploratory efficacy endpoints will be investigated.

Exploratory efficacy endpoints will be analyzed over the combined treatment period with ponesimod within studies AC-058B201 and AC-058B202 (i.e., starting from the first administration of ponesimod and ending with the EOT visit 2 or 3, as applicable). For "changes from baseline to all assessments" as well as for all numerical endpoints, all assessments available after initiation of ponesimod are considered in the combined treatment period. For time to event endpoints, the start is defined as initiation of study treatment, and patients without events are censored at the end of the combined treatment period.

The following exploratory endpoints will be analyzed:

- 1. Annualized confirmed relapse rate.
- 2. Time to first confirmed relapse.

Definition of relapse

A relapse is defined as the occurrence of an acute episode of one or more new symptoms, or worsening of existing symptoms of MS, not associated with fever or infection, and lasting for at least 24 hours after a stable period of at least 30 days.

A "confirmed relapse" is a relapse accompanied by an increase from the previous clinically stable assessment (i.e., performed at least 30 days after the onset of any previous relapse) of at least 0.5 point in the EDSS score, or one point in the score for at least one of the FS scores, excluding the bowel and bladder, and mental FS. The confirmatory EDSS must be performed within 7 days of the onset of a new symptom or worsening of an existing symptom of MS.

Symptoms of transient neurological worsening that do not meet the criteria for "confirmed relapse" because unaccompanied by objective findings, but still judged to constitute a relapse by the treating neurologist, will be recorded as "unconfirmed relapse" and included in the number of total relapses.

Confirmed and unconfirmed relapse will be recorded in the CRF. Start/end date and dose of corticosteroid treatment will also be recorded in the CRF.

Ponesimod / ACT-128800 / JNJ-67896153 Multiple Sclerosis		EudraCT 2009-011470-15 EDMS-ERI-206617631
Protocol AC-058B202	Confidential	
Version 12		
15 March 2022, page 75/179		

For exploratory efficacy endpoints both confirmed and total relapses are analyzed.

The severity of relapse will be calculated for each relapse according to the algorithm defined in Table 7.

Mild relapse	Moderate relapse	Severe relapse

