EDSS increase of 0.5 point or 1-point increase in 1 to 3 FS*	EDSS increase of 1 or 2 points or 2-point increase in 1 or 2 FS* or 1-point increase in 4 or more FS*	Exceeding moderate relapse criteria: EDSS increase of 2.5 points or 2-point increase in 3 FS* or 3-point increase in 1 FS* or 2-point increase in more than 2 FS*

Table 7:Severity of relapse

* excluding the bowel and bladder, and mental FS.

Note: The EDSS increase is the increase observed at the EDSS assessment associated with the relapse, as compared the preceding EDSS assessment (performed prior to the relapse).

3. Time to 24-week confirmed disability progression up to end of the study.

Disability progression is defined as an increase of at least one full point in the EDSS score (or 1.5 points if the baseline EDSS was 0, or 0.5 points if the baseline EDSS was equal or greater than 5.5) with or without relapse, confirmed at the next scheduled EDSS assessment at least 24 weeks later (or if missing, at the next available scheduled EDSS assessment). The time to event is defined as the time from initiation of study treatment until the first EDSS assessment meeting the criteria for disability progression.

- 4. Other relapse-related endpoints:
 - Annualized total relapse rate.
 - Time to first (total) relapse.
 - Number of (confirmed and total) relapses.
 - Number of patients without any (confirmed and total) relapse.
 - Number of patients with a relapse requiring corticosteroid treatment.
- 5. MRI-related endpoints:

Confidential

EudraCT 2009-011470-15 EDMS-ERI-206617631

- Number of Gd+ lesions per patient recorded on T₁-weighted MRI scans at all assessments.
- Number of patients with no Gd+ lesions on T₁-weighted MRI scans at all assessments.
- Total volume of Gd+ lesions per patient on T₁-weighted MRI scans at all assessments.
- Number of new or enlarging lesions per patient on T₂-weighted MRI scans at all assessments.
- Change from baseline to all assessments in total lesion volume per patient on T₂-weighted MRI scans.
- Number of combined unique active lesions (Gd+ lesions plus new or enlarging T₂ lesions without gadolinium-enhancement) per patient on MRI scans at all assessments.
- Percentage change of brain volume from Visit 2 (from AC-058B201) up to the end of the study.
- Percentage change of brain volume from Visit 11 (from AC-058B201) up to the end of the study.
- 6. Neurological endpoints:

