5.1.3. Planned Pregnancy Interruptions

Planned pregnancy interruptions will be excluded for definition of exposure, treatment-emergent adverse events and other safety variables including AEs, laboratory tests, pulmonary function tests (PFTs), vital signs and ECGs.

Planned pregnancy interruptions will not be excluded for efficacy analyses or for study duration.

Interruptions for planned pregnancies are identified in the database as defined in Section 5.2.1.5. Determination of the period of planned pregnancy interruption is described in Section 5.1.4.

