**** For ECG and Vital Signs (VS), Day 1 post-baseline assessments are also considered.

Except for last-on-treatment and last FU analysis visits, if more than one assessment falls in the same time window, the closest non-missing assessment to the target day will be taken (if equidistant then the earlier value is taken). Last-on-treatment and last FU analysis visits are always mapped to the last non-missing assessment within the window.

FU visits are derived separately from treatment-emergent visits and may result in additional records in the ADaM datasets (or flagging). Last on-treatment and FU visits are defined for AP3 only.

5.1.9. Analysis strategy for long-term safety and efficacy – analysis over the whole ponesimod period

To investigate the long-term safety and efficacy of ponesimod, analysis is performed over the combined core/TP1/TP2/TP3 periods (excluding the placebo period for subjects who received placebo in the core study). All data for all subjects who received at least one dose of ponesimod at any time are included. Analyses are performed by first randomized dose of ponesimod.

The following analysis periods are defined to support the objectives as defined in Section 1.1 and Analysis Strategy as defined above. This SAP focusses on AP3, however AP1 and AP2 are described here for historical continuity with previous analyses. See Figure 1 for an illustration of the treatment periods.

- Analysis Period 1 (AP1) (Core TP1): analyses over core and extension TP1 periods combined;
- Analysis Period 2 (AP2) (Core TP2): analyses over core, extension TP1 and TP2 periods combined;
- Analysis Period 3 (AP3) (Core TP3): analyses over all periods combined.

The placebo period is excluded from all analyses described in this SAP, however the placebo visits and events are kept in the pooled B201/B202 analysis data model (ADaM) datasets. All analyses are performed by first randomized dose of ponesimod, i.e., ponesimod 10 mg, ponesimod 20 mg and ponesimod 40 mg. Additional disposition tables are provided including the placebo arm in order to provide a complete overview of the transition of patients through the two studies as shown above.

Analysis Period	Start Date	End Date
AP1	Ponesimod start date	Minimum of [last study date, date of first administration of ponesimod in TP2 - 1 day]
AP2	Ponesimod start date	Minimum of [last study date, date of first administration of ponesimod in TP3 - 1 day]
AP3	Ponesimod start date	Last study date

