5.3.1.3. Time to first confirmed/any relapse up to end of the Analysis Period

Time to first confirmed release is derived for AP3 as follows:

The time to first confirmed relapse (in days) is defined as [Date of first confirmed relapse - ponesimod start date + 1] in days.

Subjects without any confirmed relapses during the Analysis Period are censored, and censored time is defined as the Analysis Period end date - ponesimod start date + 1, in days. In the listings censoring is displayed as 'End of Analysis Period' for subjects who did not have a relapse by the end of the Analysis Period. Relapses are labelled as either 'Confirmed Relapses' or 'Unconfirmed Relapses'.

The definition above is also applied for the derivation of time to first 'any' relapse for AP3, i.e., including confirmed and unconfirmed relapses.

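### ARR and time to first relapse run to end of study although the protocol stops them at EOT, and the only on-treatment relapse analysis is dropped from the Final CSR

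*SAP*

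**What the plan says.** **Protocol.** Section 3.10.1 sets the efficacy period as "starting from the first administration of ponesimod and ending with the EOT visit 2 or 3, as applicable". For time-to-event endpoints, "patients without events are censored at the end of the combined treatment period". Within the same section the disability endpoint is worded differently: "Time to 24-week confirmed disability progression up to end of the study".

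**SAP.** Section 5.1.9 restricts the Final CSR to AP3, and Table 4 ends AP3 at the "last study date". Section 5.1.1 defines that as the EOS date. ARR counts relapses and observation time to that date (5.3.1.1). For time to first relapse, "censored time is defined as the Analysis Period end date - ponesimod start date + 1, in days". Section 5.3.1.2 acknowledges that "the Analysis Period end date may be up to 90 days after last intake of ponesimod in the Analysis Period" and specifies an on-treatment ARR capped at last treatment + 7 days. Sections 5.3.1.2 and 5.3.2.4 then say it was done at the interim and will not be done for the Final CSR.

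**Pregnancy.** SAP 5.1.3 states: "Planned pregnancy interruptions will not be excluded for efficacy analyses or for study duration". The same section removes these interruptions from exposure and safety.

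**The concern.** The objective is the long-term efficacy of ponesimod. Under the SAP, a relapse up to 90 days after the last study dose counts in the ponesimod ARR, and the by-year ARR still describes its intervals as years of ponesimod treatment. Protocol 1.3.2.2 reports that lymphocyte counts return to baseline levels within one or two weeks of stopping. SAP Appendix 2 says the new post-treatment ARR was added to look at disease reactivation. So the sponsor regards reactivation as possible, yet leaves that time inside the main relapse figures and removes the version without it.

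The reason given for the removal is weak. The interim cut-off was 31 March 2019 with the study still running. Patients on drug at that date had no post-treatment tail then; they acquire it only in the final data. The interim result therefore cannot show how far the two versions differ at the end, and relapse data after the cut-off never receive an on-treatment analysis.

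**Working it through.** **1. Which endpoints depart from the protocol?**

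| Endpoint | Protocol 3.10.1 | SAP | Departure? |
|---|---|---|---|
| ARR | first ponesimod dose to EOT | to EOS | yes, not in Appendix 2 |
| Time to first relapse | censored at EOT | censored at EOS | yes, not in Appendix 2 |
| 24-week CDA | general rule EOT, endpoint text end of study | onset accepted up to EOS | no; the protocol is in tension with itself |

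Appendix 2 lists the dropped +7-day ARR and the pregnancy rule. It justifies AP3 as covering all of ponesimod treatment, but does not say that AP3 runs past it.

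**2. Length of the tail.** Protocol 3.1.1 gives a maximum study duration of 649 weeks. Check: 636 + 90/7 = 648.9, which rounds to 649. Follow-up after the last dose is 30 days for TP1 (EOS2) and 90 days for TP2/TP3 (EOS3). The FU3 window of ±7 days would allow 97.

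**3. Share per patient.** Share = tail / (time on drug + tail), with 30 days = 0.0821 years and 90 days = 0.2464 years. Visit P1 falls 12 weeks after Week 48 of TP1 at the earliest. That is 60 weeks of ponesimod for placebo switchers and 24 + 60 = 84 weeks for those on ponesimod since the core study. An extension patient stopping at 1 year is therefore still in TP1 and has the 30-day tail.

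- 1 year: 0.0821 / 1.0821 = 7.6%
- 2 years, in TP2: 0.2464 / 2.2464 = 11.0% (if still in TP1, 0.0821 / 2.0821 = 3.9%)
- 8.02 years (the 20 mg median at the interim): 0.2464 / 8.2664 = 3.0%

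**4. Group level, 20 mg.** From protocol 1.3.2.3 and 1.3.2.4: ARR about 0.15 and 817 subject-years. Assumed: 0.15 is the on-drug rate; 100 to 155 subjects each have a full 90-day tail; the post-treatment rate r is 0.05 to 0.6 per year.

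Tail time: 100 × 0.2464 = 24.6 years; 155 × 0.2464 = 38.2 years (2.9% and 4.5% of the total).

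ARR = (0.15 × 817 + r × tail) / (817 + tail):

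| r | 100 subjects | 155 subjects |
|---|---|---|
| 0.05 | (122.55 + 1.23) / 841.6 = 0.147 | (122.55 + 1.91) / 855.2 = 0.146 |
| 0.6 | (122.55 + 14.78) / 841.6 = 0.163 | (122.55 + 22.92) / 855.2 = 0.170 |

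**5. Can the on-treatment ARR be recovered from what remains?** The AP3 ARR is by dose (SAP 5.3.2.1). The post-treatment ARR starts 16 days after the last dose and is summarised by post-treatment DMT subgroup, with no dose split stated (5.3.2.2). Subtracting one from the other gives, at best, a crude figure pooled over doses to about last dose + 15 days. A by-dose rate with a confidence interval cannot be obtained that way.

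**The case against.** The SAP does not hide its approach. Section 1.2.3 says its treatment periods include time on and off drug, and section 5.3.5.2 says efficacy follows an intent-to-treat approach, though only in a remark on EDSS visits. The dropped ARR is logged with a reason, post-treatment relapses are tabulated separately, and every relapse is listed. All analyses are exploratory, so no error rate or decision rule is affected. If disease does reactivate, the tail works against ponesimod. All of this stands, and it is why the to-EOS results should be kept. It does not supply the missing declaration or the missing by-dose estimate.

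A reader might infer several stronger points that the documents do not support:

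- **CDA run to EOS breaches the protocol.** The endpoint's own wording runs to the end of the study. CDA censoring is also not at EOS but at the last EDSS assessment without an increase (SAP 5.3.5.1).
- **Keeping pregnancy interruptions breaches the protocol.** An interruption followed by restart lies between first dose and EOT, and the rule is logged in Appendix 2. The +7-day cap would not have removed it. What remains is an inconsistency within the SAP: up to 81 weeks (567 / 365.25 = 1.55 years), during which interferon beta-1a and glatiramer acetate "are allowed only during study drug interruptions for planned pregnancy", count for efficacy but not for exposure or safety.
- **The whole tail is off ponesimod.** Commercial ponesimod may start the day after the last study dose (protocol 3.11.5.3), and those patients still complete follow-up.
- **Relapses are double-counted.** They appear in two tables with different stated periods; no single estimate counts them twice.

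**Conclusion.** The point holds for ARR and time to first relapse. The SAP moves the end of the efficacy period from EOT to EOS without declaring it, and the Final CSR loses its only on-treatment relapse estimate by dose. The size is modest: 3% of observed time for long-stayers, up to 11% for a patient stopping at 2 years, and a group ARR of roughly 0.146 to 0.170 against 0.15.

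That range is a scenario. The number of subjects with a full tail and the post-treatment rate are assumed, and the documents do not say that the interim 0.15 is an on-treatment rate. The direction depends on whether the post-treatment rate is above or below the on-drug rate, so a claim that the reported ARR must be too high is not supported. Nor is a 90-day tail at 1 year of treatment, because such a patient is in TP1 with 30 days of follow-up.

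**What to change.** 1. Reinstate for the Final CSR the ARR to last treatment + 7 days, for confirmed and for all relapses, by dose. Add time to first relapse with the same cut. Present both as supplementary on-treatment analyses. The cut is close to the protocol's EOT visit, which falls 1 day after the last dose for completers and at most 5 days after it for early discontinuers.
2. In these analyses remove the planned-pregnancy interruption periods already derived in SAP 5.1.4, in line with exposure and safety.
3. Keep the to-EOS results, label them intent-to-treat (treatment policy), and reword the by-year ARR as years since first ponesimod dose.
4. Add an Appendix 2 entry for the move from EOT to EOS, with its rationale.
5. For CDA, do not impose the +7-day cut as if it matched the protocol. Reconcile the general EOT rule in protocol 3.10.1 with the end-of-study wording of the CDA endpoint, and state which one the SAP follows.

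The cost is a few extra tables in an exploratory report and a short SAP edit. The +7-day derivation is already specified and was run at the interim, and the pregnancy periods are already defined.

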5.3.1.3. Time to first confirmed/any relapse up to end of the Analysis Period

Time to first confirmed release is derived for AP3 as follows:

The time to first confirmed relapse (in days) is defined as [Date of first confirmed relapse - ponesimod start date + 1] in days.

Subjects without any confirmed relapses during the Analysis Period are censored, and censored time is defined as the Analysis Period end date - ponesimod start date + 1, in days. In the listings censoring is displayed as 'End of Analysis Period' for subjects who did not have a relapse by the end of the Analysis Period. Relapses are labelled as either 'Confirmed Relapses' or 'Unconfirmed Relapses'.

The definition above is also applied for the derivation of time to first 'any' relapse for AP3, i.e., including confirmed and unconfirmed relapses.

5.3.1.4. Annualized relapse rate in the Post-treatment-emergent period

The following variables are derived for the analysis of ARR in the post-treatment-emergent period:

- Number of confirmed/all relapses with start date in the post-treatment emergent period; i.e. date of last administration of ponesimod plus 16 days, as defined in Section 5.1.6;
- Length of observation for the post-treatment-emergent period as defined in Section 5.1.6, expressed in years.

5.3.1.5. Other relapse-related characteristics

Relapses requiring hospitalization and relapses requiring treatment with corticosteroids are flagged in the ADaM dataset.

The need for hospitalization and treatment with corticosteroids is stored in SUPPCE. Any corresponding medications administered are recorded in SDTM.CM with CMCAT = "CORTICOSTEROIDS (IV) FOR TREATMENT OF RELAPSE".

In the legacy paper CRF, the question related to hospitalization for relapse was '*Relapse lead to* hospitalization of patient?' with responses "Yes" or "No". The reason for hospitalization was captured as a query response in free text. In RAVE, the question was amended to '*Relapse led to* hospitalization of patient (for reasons other than administration of IV corticosteroids (e.g., relapse severity or medical complications due to relapse)' with responses "Yes" or "No". There is a potential discrepancy between the response "Yes" to the question in the legacy CRF and the question in RAVE, since hospitalizations recorded in the legacy CRF would also include patients admitted only for the administration of corticosteroids.

Given this limitation, relapses requiring hospitalization will not be included in the summary tables due to the inconsistencies between the legacy CRF and RAVE described above, i.e., hospitalizations recorded originally in the legacy CRF also include patients admitted only for the administration of corticosteroids". However, the full characterization, including hospitalization, will be included in the listings.

CONFIDENTIAL – FOIA Exemptions Apply in U.S.

Relapse severity is derived for each relapse according to the algorithm defined in Table 6.

Table 6: Seve	rity of	relapse
---------------	---------	---------

Mild relapse	Moderate relapse	Severe relapse
EDSS increase of 0.5 point	EDSS increase of 1 to 2 points	Exceeding moderate relapse
or	or	criteria:
1-point increase in 1 to 3 FS*	2-point increase in 1 or 2 FS*	EDSS increase of \geq 2.5 points
	or	or
	1-point increase in 4 or more FS*	2-point increase in 3 FS*
		or
		3-point increase in 1 FS*
		or
		2-point increase in more than 2 FS^*

* excluding the bowel and bladder, and mental FS

FS = functional system.

The algorithm is applied by considering the EDSS assessment associated with the relapse (as linked in SDTM) relative to the last EDSS assessment that was performed prior to this linked relapse EDSS assessment and prior to the relapse. The change in EDSS score and corresponding FS scores between these two EDSS assessments is used to define the severity as classified in Table 6 above. If either EDSS assessment is missing, relapse severity is missing.

Duration of relapse (days) is derived as relapse end date – relapse start date + 1 days. Relapses with missing or partially missing end dates are not included.

